Unique to tACS is the ability to entrain underlying EEG rhythms with subsequent effects on spectral power and coherence of specific EEG frequencies (23). tACS has been demonstrated to modulate multiple domains of cognition and underlying brain networks, in a mechanism that is dependent on both frequency and location of cortical stimulation sites (reviewed in (24)). With respect to sleep modulation, tACS has been demonstrated to enhance slow wave sleep duration and quality in healthy adults, with subsequent improvement of cognitive performance in memory encoding (7, 13, 25). The use of tACS for such studies has until now relied on conventional sleep lab polysomnography for assessment of EEG and delivery of tACS. Recent innovations in EEG and tES technology, however, have now enabled both tES studies (26, 27), and EEG sleep studies (28) to be performed unsupervised in an at-home protocol. Our proposed study will utilize at-home tACS with simultaneous EEG monitoring to demonstrate feasibility in treating and assessing sleep impairment and accompanying cognitive impairment. Data and manuscripts from this work will be used to support applications for funding larger scale studies using remote treatment and assessment, and thus provide a paradigm which is more feasible to translate and implement in clinical settings.

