The PI has assisted both planning and execution of tDCS and transcranial magnetic stimulation (TMS) experiments with his primary mentor. The mentor has significant experience in the application of TMS, has ongoing tDCS experiments (COMIRB 15-1035), and has completed training in the safety and use of tDCS in healthy adults and clinical populations at the Berenson-Allen Center for Noninvasive Brain Stimulation (Harvard Medical School) and has trained numerous graduate students and clinicians in the safe application of noninvasive brain stimulation in clinical and research contexts.

IV. RESEARCH STUDY DESIGN

1. Optimization of tACS settings during sleep: In this branch of our study we will optimize our tACS delivery in normal healthy research subjects by assessing response to EEG signal during stimulation. Recent developments in tACS technique allow for analysis of data acquired during tACS,(37) and this branch of our study will utilize this novel capability to determine optimal tACS stimulation intensity, duration, and frequencies for enhancement of slow wave sleep. This will be a single night tACS treatment, and multiple variables of tACS stimulation (different intensities, durations, and frequencies) will be applied for each subject. The outcome measures will be slow wave activity power, as well as synchronization of EEG signals in our recordings before, during and after tACS.

The subjects will initially be assigned to receive tACS with frequency, intensity and duration parameters in ranges similar to published trials utilizing tACS during sleep (0.75 Hz, five minutes duration, 0.318 mA/cm²) (7, 25). Each of these tACS variables will be stepwise modulated, with multiple sets of parameters used sequentially for each subject night of sleep. EEG data will be analyzed for each stimulation condition to determine optimal response to tACS with regard to frequencies, intensity, and duration. Sequential subjects will receive iterations of optimization to allow for refinement of tACS response in EEG recorded data. We predict that measurable changes in EEG slow wave power, measured between 0.5-2 Hz, can be determined within single subjects via processing EEG data obtained during stimulation. This proposal seeks to enroll up to 52 subjects to allow for multiple cycles of optimization and repetition of parameters across multiple individuals. Optimal tACS parameters will then be applied for subsequent steps of the experiments outlined below.

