The subjects will be assigned to one of three treatment groups (tACS nested, tACS single frequency, or sham) using block randomization. Computer-generated randomization will place each subject into one of the study groups initially, then cross each subject the each other condition subsequent sessions. The primary outcome measure is induced EEG power of slow wave sleep of 0.5-2 Hz measured immediately before and after each train of stimulation. To detect a significant change ($p<0.05$) of EEG power increase $\geq 20\%$ above sham, with a power of 0.80, a sample size of 15 subjects will be necessary, based on effect sizes from prior studies (7). Subjects will receive 1 session for each stimulation type, in a cross-over design with at least 1 week between each stimulation condition for wash-out. This will total to 3 sessions for each subject, with a total of 45 sessions for all subjects. Subjects will have up to 24 weeks to complete all study sessions and complete the trial. The proposed study seeks to enroll 30 participants to account for participants that may fail our screening criteria, have unusable data or drop-out of the study before completion. Secondary outcomes will include analysis of slow wave EEG coherence, sleep spindle signal, duration of slow wave sleep, total duration of sleep, word-paired associates task and finger tapping task (7, 25), as well as subjective sleep quality reported on the Consensus Sleep Diary and Pittsburgh Sleep Quality Index (38, 39). Data collection for this study is expected to take 6 months.

4. Assessment of tACS in Older Adult Subjects: In this branch of our study, we will test older adults for response to tACS applied during NREM sleep, with outcomes of EEG data, cognitive performance assessments, as well as assessment of sleep quality, mood, and quality of life measures. In addition, subjects will be screened for decisional capacity via the UCSD Brief Assessment of Capacity to Consent (UBACC), and subjects who are found to have impaired capacity will require a legally authorized representative for consent (40).

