Name of Instrument/tool/procedure	Purpose (i.e. what data is being collected)	Time to complete
Post-procedure questionnaire	Assess for tolerability of device and address any safety concerns	15 minutes
HADS	Assess anxiety and depression (to be administered for MCI trial)	5 minutes
CGIC	Assess Global Impression (to be administered for MCI trial)	5 minutes
Collection of Sleep Diary and Equipment	Collect and Inventory Instruments and Hardware	15 minutes
Total time		30-40 minutes

VISITS THREE and FIVE

Name of Instrument/tool/procedure	Purpose (i.e. what data is being collected)	Time to complete
EEG/tACS Equipment Distribution	Ensure subjects remember proper equipment use	20 minutes
Total time		20 minutes

Location

Pre- and post-test sessions will occur in Building 500 of the Anschutz Medical Campus. Testing will occur at the subjects' homes.

tACS Procedure

tACS or sham will be administered using the StarStim stimulator. Anodes of the tACS stimulator will be placed bilaterally at frontal positions on a 10-20 EEG Electrode Placement System and the cathodes will be placed bilaterally on the posterior regions. Oscillating stimulation, ranging between 0 mA to 2.0 mA (maximum current density 0.515 mA/cm²) will be applied through electrodes in trains up to ten minutes, at frequencies between 0 to 500 Hz in the tACS treatment groups while subjects are in stable stage 2 or deeper NREM sleep on EEG recording (total stimulation time not to exceed 60 minutes). This is similar to prior tACS sleep studies which have safely utilized stimulation protocols within this frequency range (7, 46-48). Our maximum current density is within guidelines of established protocols, and is well below safety thresholds of 14.29 mA/cm² from data obtained in animal models (49). All stimulation

parameters are well below currently accepted safety guidelines for tACS (50). Sham condition will be application of electrodes, without activation of current stimulation. The StarStim tACS device is designed to turn on and off automatically, without need for subject control.

XIII. SPECIMEN MANAGEMENT

There will be no specimens taken in this study.

XIV. DATA MANAGEMENT

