Official Title: Application of Transcranial Alternating Current Stimulation for Modulation of Sleep and Cognitive Performance

NCT03112902

June 6th, 2021

Statistical Analysis Plan: For each arm, we will perform a three-arm cross-over design to determine whether there is a significant group difference between each tES condition as measured in EEG power in 0.5-2 Hz frequency following tES using repeated measures ANOVA. Recruitment of 15 subjects, with cross-over intervention (*sample size* 15) will allow us to detect differences between groups with an effect size of Cohen's  $d = 1.2$ , power of 80%, and significance of 0.05. This is based on sample sizes and effect sizes reported with motor network tES. Planned secondary analyses of each arm will include scores of slow wave EEG coherence, slow and fast spindle numbers, total duration of each sleep stage, changes in slow wave coherence, changes in slow wave power, self reported sleep timing changes, changes in anxiety and depression (measured by HADS), changes in clinical global impression of change (CGIC), and cognitive performance data, including assessment of procedural memory, verbal (declarative) memory encoding, attention/working memory/visuospatial processing using repeated measures ANOVA of the data.

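### The SAP's post-stimulation-only primary quantity is open to drift over the night, because the number and timing of trains follow sleep that tACS may itself change

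*Protocol*

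**What the plan says.** **Delivery.** Protocol section XII (tACS Procedure) says that current "will be applied through electrodes in trains up to ten minutes", and only "while subjects are in stable stage 2 or deeper NREM sleep on EEG recording (total stimulation time not to exceed 60 minutes". It sets no fixed or minimum number of trains, and no clock time or sleep cycle for them.

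**Sham.** The same section says: "Sham condition will be application of electrodes, without activation of current stimulation". Neither document says how sham windows are triggered or time-stamped.

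**Primary outcome.** Protocol sections IV.3 (healthy 18-50) and IV.4 (older adults) name "induced EEG power of slow wave sleep of 0.5-2 Hz measured immediately before and after each train of stimulation". Section IV.5 (MCI) is nearly identical.

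**Primary analysis.** The SAP compares conditions "as measured in EEG power in 0.5-2 Hz frequency following tES using repeated measures ANOVA". It gives no pre-train value, no train number or time of night, and no rule for turning several trains into the analysed value.

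**Possible effect on sleep.** Protocol section II states that "tACS has been demonstrated to enhance slow wave sleep duration and quality in healthy adults", and the SAP lists the duration of each sleep stage among its secondary analyses. The plan therefore allows that stimulation changes the sleep that governs later trains.

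**The concern.** Train count and timing are post-randomisation quantities that treatment may affect. Each cross-over subject has one night per condition, so a single night sets that subject's trains under each condition. Randomising the order of nights balances chance variation in train count. It does not balance a shift that stimulation itself causes, or one that arises because sham windows are placed by another rule.

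Suppose slow wave power falls as the night goes on. A post-train average over fewer, earlier trains is then higher than one over more, later trains, even with no treatment effect. Fewer trains on tACS nights would look like benefit, and more trains would mask benefit. The before-train reading that the protocol collects would largely remove this, but the SAP's stated quantity leaves it out.

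**Working it through.** **The plan's own figure.** The SAP's 15 subjects for 80% power at d = 1.2 can be reproduced. Take a three-condition repeated measures ANOVA with means 0, 0.6 and 1.2 SD and zero within-subject correlation. The noncentrality is 15 × (0.6² + 0 + 0.6²) = 10.8 on F(2, 28), and power is 80.2%. Those choices are not stated in the SAP. The sample size is not in dispute here.

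**How far the train count can vary.** With ten-minute trains the cap allows 60/10 = 6. With five-minute trains, the starting length in section IV.1 ("0.75 Hz, five minutes duration"), it allows 60/5 = 12. No lower limit is given.

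**Assumed inputs (not in the documents).**
- Power falls by a fraction d per successive train, with d = 5% or 10%.
- There are 15 paired differences on the log scale and a two-sided 5% t-test, so 2.5% in favour of tACS under the null.
- The SD of the difference is the value at which the protocol's 20% target has 80% power with 15 pairs. The detectable standardised difference is 0.778, so SD = ln(1.2)/0.778 = 0.1823/0.778 = 0.234.

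**Spurious difference with no true effect.** The mean over the first K trains is M(K) = (1/K) Σ (1−d)^(k−1), k = 1 to K. The bias is ln[M(K tACS)/M(K sham)], and the noncentrality is bias × √15 / 0.234.

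| d | M(5) | M(6) | M(5)/M(6) | Noncentrality | False positives favouring tACS |
|---|---|---|---|---|---|
| 5% | 0.9049 | 0.8830 | 1.025 (+2.5%) | 0.40 | 5.7% |
| 10% | 0.8190 | 0.7809 | 1.049 (+4.9%) | 0.79 | 11.0% |

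**Opposite direction, true increase 20%, 6 tACS against 5 sham trains.**
- d = 5%: 1.2 × 0.8830/0.9049 = 1.171. Observed increase 17.1%, noncentrality 2.61, power 68%.
- d = 10%: 1.2 × 0.7809/0.8190 = 1.144. Observed increase 14.4%, noncentrality 2.23, power 54%.

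Both compare with a planned 80%.

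**Simulation.** There were 1,000 runs per setting with 15 subjects and 3 to 6 trains per night. Log SDs were assumed: subject 0.25, night 0.15, window 0.15. There was no carry-over between trains. Rejection is two-sided at nominal 5%.

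| No true effect, 10% decline per train | Post-train mean: difference, rejection | Per-train before/after change: difference, rejection |
|---|---|---|
| Same count distribution on both nights | +0.2%, 3.7% | −0.1%, 4.8% |
| One fewer train on tACS nights | +5.3%, 11.2% | +0.1%, 5.0% |
| One more train on tACS nights | −3.8%, 8.1% | −0.1%, 5.2% |

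With a true 20% effect, 10% decline and one more tACS train, the post-train estimate falls to 15.2% and its power from 74% to 53%. The before/after change stays at 20.0%. The absolute power values depend on the assumed SDs and are not estimates for this trial.

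**The case against.** The strongest reply is that the protocol already holds the remedy: it measures power "measured immediately before and after each train of stimulation". On that reading the SAP sentence is only a loose summary. Repeated measures ANOVA could also carry train, or before/after, as a further within-subject factor, and the SAP does not exclude this. That is fair, and it is why the point is conditional. But the SAP's stated quantity is power after stimulation, and its reference to changes in slow wave power appears only among the secondary analyses.

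The further objections also have weight:
- **Bias needs a systematic shift.** Equal count distributions on the two nights give no bias, as the simulation shows.
- **Direction.** The protocol's own background points to longer slow wave sleep, hence more tACS trains and a conservative error. The tingling and itching listed in section XVI are general reports for electrical stimulation, not stated to come from sleeping subjects, so they are weak support for fewer trains.
- **Size.** The 60-minute cap may equalise counts on nights that reach it. If only half the subjects lose one of six trains, the bias halves on the log scale. The apparent increase is then √1.025 − 1 = 1.2% at 5% decline and √1.049 − 1 = 2.4% at 10%, with false-positive rates of 3.8% and 5.6%.
- **Records exist.** Section XVII plans a review of session logs and EEG verification of delivery, so the trains actually given can be counted.

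Comparing equal train numbers is not a full cure either, because equal numbers need not fall at equal times of night. If four tACS trains are spaced 1.5 times further apart than four sham windows, the mean of (1−d)^(1.5k), k = 0 to 3, over M(4) is 0.8943/0.9275 at 5% decline and 0.8013/0.8598 at 10%. Those are spurious differences of −3.6% and −6.8%.

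**Conclusion.** The point holds as a conditional weakness in the SAP. The primary quantity it states drops the pre-train reading that the protocol makes part of the outcome, and it is exposed to drift over the night if tACS moves the trains. A one-train systematic shift with a 5-10% decline per train gives a spurious difference of 2.5-4.9%, well below the 20% target but enough to raise the 2.5% error rate to 5.7-11.0%. The decline, the shift and the SD are all assumptions. A larger SD would lower these rates and a smaller one would raise them.

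A reader might infer that the plan averages whatever trains occurred each night, and so certainly compares different parts of the night on tACS and sham, in favour of tACS. The documents do not support that. Neither describes such a nightly value, neither shows that train counts differ by condition, and the direction suggested by the protocol's background is the conservative one.

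**What to change.** Change the SAP and leave the stimulation rule alone.

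1. Align the primary quantity with the protocol by analysing the per-train log(after/before) change. Alternatively, analyse log post-train power per train in a mixed model with condition, period (cross-over branches only), train position or time since sleep onset, power before the first train, and night within subject as a random effect. In the MCI branch, take power before the first train from the first night, since later nights follow earlier stimulation.
2. State which of the two is primary and report the other alongside it. From the second train on, the before-reading follows earlier stimulation, so the per-train change does not capture carry-over from earlier trains. The post-train model can show it.
3. Place and time-stamp sham windows by the same sleep trigger as active trains.
4. Tabulate trains and stimulated minutes per night by condition, and say in advance how nights with few or no trains are handled.

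The cost is SAP wording and slightly more programming. The before and after EEG is already collected, and the sample size need not change on this account.

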- 3). Determine effects of tACS delivered with nested frequencies(multi-frequency signal) vs single frequency tACS, with regard to intrinsic EEG signal, for modulation of SWA coherence and power, as recorded in our overnight EEG sleep data.
- 4). Determine the cumulative effects of tACS delivered in multiple, consecutive nights on underlying EEG signals, sleep architecture, sleep quality and cognitive function among patients with MCI.

5). Determine if tACS is a viable treatment for disturbances of sleep and cognitive performance among patients with MCI.

6). Generate pilot data and manuscripts to support applications for larger randomized placebo-controlled clinical trials.

We hypothesize that through multiple and consecutive sessions, there are cumulative effects of tACS on sleep architecture, with subsequent impacts on cognitive performance, mood and quality of life among normal health adults, older adults, as well as individuals with MCI.

II. BACKGROUND AND SIGNIFICANCE

Transcranial alternating current stimulation (tACS) is a form of transcranial electrical stimulation (tES), similar to transcranial direct current stimulation (tDCS), each of which utilizes scalp electrodes to deliver current at low amperage through brain cortex. In the case of tACS this current is set to alternate in a specific frequency (14). This transcranial current flow has been demonstrated to alter cellular membrane potentials, with subsequent alteration of cortical excitability and synaptic potentiation (10). The use of tES in human trials has increased markedly within the last 15 years, and to date hundreds of trials with thousands of subjects have been reported without any serious side effects (10, 15). The benefits of tES have been demonstrated in treating the cognitive symptoms of many neurological illnesses including Alzheimer's disease, Parkinson's disease, stroke, depression and epilepsy; notably with exceptional tolerability and without any major safety concerns reported (16-22).

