This will be a randomized-controlled trial with two study arms: a tACS treatment phase and a sham treatment phase. The subjects will be assigned to one of two treatment groups (tACS vs sham) in a 1:1 ratio using block randomization. Stimulation will be applied in-phase, single frequency or nested, if indicated based on the results of experiments 1 and 2. Computer-generated randomization will place each subject into one of the study groups. The primary outcome measured is EEG power of slow wave sleep of 0.5-2 Hz, measured immediately before and after each train of stimulation. To detect a significant change ($p<0.05$) of EEG power increase $\geq 20\%$ above sham, with a power of 0.80, a sample size of 30 subjects will be necessary. Subjects will receive either stimulation type, tACS or sham, each night for the one week study period, for up to 7 stimulation sessions pending results of Experiment 2. Subjects will have up to 24 weeks to complete all study sessions and complete the trial. The proposed study seeks to enroll 35 participants to account for participants that may fail our screening criteria, have unusable data or drop-out of the study before completion.

Secondary outcomes will include analysis of slow wave EEG coherence, slow and fast spindle activity, duration of slow wave sleep, total duration of sleep, and subjective sleep quality reported on the Consensus Sleep Diary (CSD), Pittsburgh Sleep Quality Index (PSQI), mood assessment by the Hospital Anxiety and Depression Scale (HADS), overall function in the Clinical Global Impression of Change (CGIC).

Consensus Sleep Diary (CSD)

The CSD is a sleep journal instrument that is designed to measure sleep and has been validated for intervention trials in insomnia (38, 41).

Word Paired-Associate Task

Our computerized paired-associate task consists of 48 semantically related words selected from a normative database with assessment of memory encoding on recollection performance (25, 42)

Finger Tapping Task

This is a finger sequence tapping task of procedural memory. Subjects repeatedly finger-tap with their non-dominant hand a five-element sequence presented on a computer monitor, e.g. 4-2-3-1-4, as fast and accurately as possible on a key board (7).

Pittsburgh Sleep Quality Index (PSQI)

This is a 10 question questionnaire consisting of questions related to usual sleep habits (39).

The Hospital Anxiety and Depression Scale (HADS)

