All efforts will be made to protect the confidentiality of research subjects. All electronic data will be collected via REDCap, de-identified by the research team, and stored on their servers. Only study personnel will have access to the data. The dataset will be stored on a computer that is password-protected, virus-protected, and automatically logs the user off after a period of inactivity. The computer is located in a locked office. The computer will be password protected when not in use. All written data will be stored in a locked file cabinet in a private office, the research office of the Department of Neurology. All personnel involved in the study have completed HIPAA training. Any PHI will be stripped from data files (or shredded from written records) within 6 months of the end of the data collection period such that all PHI will be deleted prior to completion of the final data set. Any publication of data will be reported in aggregate.

XV. WITHDRAWAL OF PARTICIPANTS

Subjects will be withdrawn if they experience adverse effects due to tACS application or are unable to tolerate wearing of equipment. Data from subjects that withdraw will be collected and protected, but not utilized in the data analysis. Follow up will only be performed in the case of adverse events to ensure the safety of the patient.

XVI. RISKS TO PARTICIPANTS

tACS

Over 10,000 research subjects had received tES, including tACS, as of 2014, without any serious side effects reported (51). There has been no evidence of seizures, neuronal pathology, edema or neuropsychological damage (15). At-home, unsupervised, application of tES has been demonstrated to be safe and well-tolerated, without any major adverse events or safety concerns (26, 27). During administration of tES, subjects have reported a mild tingling sensation (70.6%), moderate subjective fatigue (35.3%) and a light itching sensation (30.4%). After administration of tES, subjects have reported mild transient headaches (11.8%), nausea (2.9%) and insomnia (0.98%) (52). Our stimulation parameters (maximum current density 0.515 mA/cm²) are far below established safety thresholds of 14.29 mA/cm² (49). All stimulation parameters within this proposal are well below currently accepted safety guidelines for tACS (50).

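### Section XV leaves the collected data of withdrawn subjects out of the analysis; in the MCI branch, read as parallel-group, this exclusion can differ by arm and bias tACS against sham

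*Protocol*

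**What the plan says.** Protocol Section XV gives two grounds for withdrawal: "Subjects will be withdrawn if they experience adverse effects due to tACS application or are unable to tolerate wearing of equipment". It then fixes what happens to the data: "Data from subjects that withdraw will be collected and protected, but not utilized in the data analysis". It exempts no branch. It also limits later observation: "Follow up will only be performed in the case of adverse events to ensure the safety of the patient".

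Section XII (tACS Procedure) defines the comparator: "Sham condition will be application of electrodes, without activation of current stimulation".

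Section IV.5 sets out the MCI branch: "The subjects will be assigned to one of two treatment groups (tACS vs sham) in a 1:1 ratio using block randomization", and "Subjects will receive either stimulation type, tACS or sham, each night for the one week study period, for up to 7 stimulation sessions". The number of nights is conditional on an earlier experiment. Thirty subjects are needed, and the reserve is stated as: "The proposed study seeks to enroll 35 participants to account for participants that may fail our screening criteria, have unusable data or drop-out".

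The SAP is one paragraph. It names repeated measures ANOVA, and no analysis set, missing-data method or sensitivity analysis.

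**The concern.** Dropping subjects after randomisation is harmless to the comparison only if the drop is unrelated to outcome or acts alike in both arms. Here one trigger, adverse effects of tACS, is tied to a current that only the active arm receives. The other, not tolerating the equipment, applies to both. A tACS subject can thus be removed for a reason that a sham subject cannot strictly meet.

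If those who leave also differ in slow-wave response, the remaining tACS subjects are a selected group compared with a less selected sham group. The analysis then answers a question about those who tolerated treatment, not the randomised one, and the reader cannot see how far the two differ.

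The MCI branch carries Specific Aim 4 ("Determine the cumulative effects of tACS delivered in multiple, consecutive nights on underlying EEG signals, sleep architecture, sleep quality and cognitive function") and Aim 5, on whether tACS is viable as a treatment in MCI. It also feeds the pilot data of Aim 6. Tolerability bears directly on viability, yet the rule removes the subjects who did not tolerate treatment.

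**Working it through.** **1. Is the MCI branch parallel?**

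For: Section IV.5 has 1:1 groups with one stimulation type per subject. Section XII.5 lists seven home nights. Section IX caps payment at $175 at $25 per home visit, so 175/25 = 7 visits; a cross-over with seven nights per condition would need 14.

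Against:
- Section IV.5 also calls the two arms phases.
- The SAP describes a three-condition cross-over for every branch.
- The MCI visit tables in Section XII.5 collect equipment at visits two, four and six and hand it out again at visits three and five. This matches the healthy cross-over branch and does not obviously fit one continuous week.

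The parallel reading is the better one, but it is not settled.

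**2. The plan's own figure.** Section IV.5 needs 30 subjects for 80% power to detect a 20% increase over sham. No SD is given, so this cannot be reproduced. Back-solving a two-sided 5% t-test at 15 per arm gives d = 1.06, an implied SD of 20/1.06 = 18.9 percentage points. This serves only as a scale. The reserve is 35 − 30 = 5, shared with screening failures and unusable data.

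**3. Bias from the exclusion.** Assumptions, none given in the documents: no true effect; 17 tACS and 18 sham randomised (that is, all 35); those who leave are lowest on a score with correlation ρ to outcome. If a share p of the tACS arm leaves and none of sham,

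bias (in SD) = ρ · φ(z_p) / (1 − p).

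- Two leave: p = 2/17 = 0.118, φ = 0.197, 0.197/0.882 = 0.22. Bias is 0.07 at ρ = 0.3 and 0.11 at ρ = 0.5.
- Five leave: p = 5/17 = 0.294, φ = 0.345, 0.345/0.706 = 0.49. Bias is 0.15 and 0.24.

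Simulation with exact counts removed (100,000 null trials per setting, two-sample t-test):

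| Lost, tACS vs sham | Bias in SD, ρ = 0.3 / 0.5 | Two-sided error |
|---|---|---|
| 2 vs 0 | 0.063 / 0.106 | 5.4% / 6.3% |
| 3 vs 0 | 0.086 / 0.149 | 5.6% / 7.3% |
| 5 vs 0 | 0.140 / 0.232 | 6.5% / 9.5% |
| 2 vs 1 | 0.030 / 0.052 | 5.2% / 5.8% |
| 2 vs 2 | 0.002 / 0.005 | 5.2% / 5.6% |

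Repeat runs and the formula put the upper end at 0.24 SD and 9.7%. At ρ = 0 the bias is within 0.002 SD. A negative ρ reverses the sign. For scale, 17 vs 18 detects d = 0.98 at 80% power, and 0.24 × 18.9 is about 4.5 points against the 20-point target.

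**4. What remains if collected nights are kept.** Suppose each leaver contributes m of 7 nights, nights within a subject share one intraclass correlation (ICC), and the model has condition-by-night terms. The kept nights are unbiased. On each missing night the model recovers a fraction m·ICC/(1 + (m−1)·ICC) of the shift. The share of the completers-only bias that remains is therefore

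(7 − m)/7 × (1 − ICC)/(1 + (m − 1)·ICC).

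- One night kept: 6/7 × 0.9 = 77% at ICC 0.1; 6/7 × 0.7 = 60% at 0.3; 6/7 × 0.3 = 26% at 0.7.
- Three nights kept: 4/7 × 0.9/1.2 = 43% at ICC 0.1; 4/7 × 0.3/2.4 = 7% at 0.7.

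Simulation at ρ = 0.5 agrees: 25–77% with one night kept, 8–44% with three. With five leavers and one night kept, the remainder is 0.14–0.18 SD at ICC 0.3 down to 0.1. The documents give no ICC.

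**The case against.** **The design may not be parallel.** The SAP is the later document (2021 against 2019) and describes a cross-over throughout; the MCI visit tables point the same way. If that governs, a withdrawn subject leaves every condition at once and the between-arm mechanism goes. This stands as a limit on the point: the passages must be reconciled.

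**The effect is small in moderate cases.** Two losses against one leave the error at 5.2–5.8%. Complaints in sham subjects may also be put down to tACS, which would shrink the imbalance. This stands too, and for a pilot it argues against treating the point as fatal. It does not justify setting aside data already in hand.

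**The remedy is partial, and its detail goes beyond the defect.** The defect is the analysis set. But classical repeated measures ANOVA drops any subject who lacks a condition, so a new analysis-set sentence alone could not be carried out with the SAP's model.

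**Stronger readings a reader might infer, which the documents do not support:**
- That the rule favours tACS. The sign follows the correlation between leaving and outcome, which is not given.
- That five losses is the worst case. It uses up the 35-to-30 reserve, but nothing caps withdrawals, and fewer than 35 may be randomised.
- That keeping the nights removes most of the bias. That depends on the ICC and on how early subjects leave.
- That the cross-over branches are biased in the same way. There the whole subject is removed, so conditions stay balanced within subjects. The cost is lost nights and a result limited to those who tolerated treatment. Enrolment of 30 and 35 for 15 needed makes the loss of precision secondary.

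**Conclusion.** The point holds and should be fixed. Section XV is an explicit rule to set aside collected data, nothing in the SAP overrides it, and in the MCI branch read as parallel it can act unequally on the arms.

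Bias is possible, not certain. It requires both unequal withdrawal and a link between withdrawal and outcome, and its direction is unknown. Under the stated assumptions it runs from near zero (balanced or unrelated losses) to about 0.06–0.24 SD with 5.4–9.7% two-sided error (two to five tACS-only losses). These figures illustrate; they are not bounds. Confidence is medium, because the withdrawal rates, the correlation and the MCI design itself are not settled by the documents.

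**What to change.** - **Section XV:** replace the data sentence with one saying that all usable data collected up to withdrawal are analysed in the assigned group or sequence. State the same analysis set in the SAP. The withdrawal criteria stay as they are.
- **MCI model:** a mixed model (REML, random subject effect) of the nightly outcome with condition, night and condition-by-night terms. State the target in advance, for example the mean over the number of nights finally set. The interaction matters because Aim 4 expects effects to build up. With an effect rising from 0 to 1 SD over seven nights (true mean 0.50) and ICC 0.5–0.7, a constant-effect model gives 0.43–0.45 when five tACS subjects leave early; the interaction model gives 0.50.
- **Cross-over branches:** replace classical repeated measures ANOVA with a mixed model as well, or limit the new rule to MCI.
- **Reporting:** give withdrawals and reasons by arm, and keep completers-only as a sensitivity analysis.
- **Design:** reconcile Section IV.5, the MCI visit tables and the SAP on whether the MCI branch is parallel.

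The cost is a sentence in Section XV, an analysis-set sentence and model lines in the SAP, with no new data or sample size. At ICC 0.5–0.7 the interaction raises the standard error by at most 0.5% over the constant-effect model.

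Limits: follow-up stops at withdrawal except for adverse events, so this is an available-data analysis under missing at random, not full intention to treat. Subjects with no usable stimulation train still cannot contribute, and late-night estimates rest on fewer subjects.
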